11. STUDY EVALUATIONS

11.1. Study Procedures

The Schedule of Assessment included in the synopsis summarizes the frequency and timing of the study procedures. Data collected for the patient during the study will be recorded in the patient's medical records, and study worksheets/source documents, as appropriate, and will be transcribed into the eCRF.

11.1.1. Visit 1 (between Day -21 and Day -1 before Surgery) – Screening Visit

Prospective patients will be screened within 21 days prior to surgery. Prior to performing any study activities/evaluations, the patient must be thoroughly informed about all aspects of the study, including scheduled study visits and activities, and must sign the informed consent form. Signed

copies of the informed consent forms should be given to the patient. During this visit the patient will be assigned a screening number by the Investigator in sequential order.

During the visit, the Investigator will collect the following information, which will be recorded in the study eCRF and study file (when required):

- Informed Consent collection.
- Allocation of screening number.
- Demography / Medical history.
- Physical examination.
- Vital signs (blood pressure, heart rate, temperature, respiratory rate).
- Pregnancy test (β -HCG urine test) for female patients of childbearing potential.
- Blood hematology and biochemistry (see Schedule of Assessments for the list of tests).
- Measurement of coagulation parameters (PT, PTT, INR).
- Urine analysis (see Schedule of Assessment for the list of tests).
- Levels of antibodies against Human Fibrinogen and Human Thrombin. For this purpose, a serum sample will be collected and stored at -70°C for testing at the end of the study.
- MRI assessment of the intervention site. Additional MRI will be performed throughout the study if the investigator identifies signs and symptoms of unanticipated or unexpected persistent inflammatory response, or unexplained abdominal pain or other symptoms (for instance signs of adhesions, bowel obstruction, etc.).
- An additional serum sample will be collected and stored at -70°C for possible future viral safety testing.
- Eligibility Criteria evaluation. In the event that a Patient is not eligible, the reason will be documented on the eCRF and screening log.
- Concomitant Medications.

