11.1.6. Visit 6 (Day 30±3 after surgery) – Follow up Visit #1

The following information will be recorded at the clinical follow-up visit approximately one month following surgery:

- Physical examination and documentation of any changes in medical history.
- Vital signs (blood pressure, heart rate, temperature, respiratory rate).
- Blood hematology and biochemistry (see Schedule of Assessments for the list of tests).
- Measurement of coagulation parameters (PT, PTT, INR).
- Urine analysis (see Schedule of Assessment for the list of tests).
- Testing of antibodies levels (against Human Fibrinogen and Human Thrombin).
- Adverse events (in particular related to post-operative adhesions, systemic inflammation, bleeding / thrombotic and transfusion-related complications).
- Transfusion requirements.
- Concomitant medications.

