3.3 Study Endpoints

3.3.1 Primary Endpoint

The primary endpoint of the study consists of multiple safety variables as a composite marker for the safety. Variables of the composite marker were assessed during all study periods: from randomization to end of follow-up. It includes evaluation of treatment emergent adverse events (TEAEs), particularly TEAEs related to bleeding at TBS, thrombotic events, transfusion-related complications, post-operative adhesions (MRI assessment). It also includes evaluation of vital signs, physical examination, urine analysis, blood/coagulation parameters profiles, antibodies against fibrinogen and thrombin, and signs of systemic inflammation.

Primary endpoint is considered as a composite endpoint, because it includes multiple explanatory variables that support safety and tolerability of study treatment on the efficacy claim.

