6.5 Handling of Missing Values

In accordance with the Study Protocol, no substitution or specific approach for missing data will be applied.

	STATISTICAL ANALYSIS PLAN	FSTAT.01.03
Study Code: HEM-HEM-01-17		Sealantium Medical Ltd.

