6.12 Safety Evaluation

As previously stated, Safety is the primary endpoint.

Safety could be a composite endpoint because include more than one variable:

- ✓ Adverse Events
- ✓ Thrombotic Events
- ✓ Transfusion-Related Complications
- ✓ MRI Assessment (post-operative adhesions)
- ✓ Signs of Systemic Inflammations
- ✓ Antibodies against Fibrinogen and Thrombin
- ✓ Physical Examination
- ✓ Vital Signs
- ✓ Blood and Coagulation Parameters
- ✓ Urine Analyses

All Safety data will be listed by patients and treatment groups at each collected time and tabulated with the appropriate descriptive statistics by treatment groups at each collected

	STATISTICAL ANALYSIS PLAN	FSTAT.01.03
Study Code: HEM-HEM-01-17		Sealantium Medical Ltd.

time.

Considering that no hypothesis testing for difference between treatments groups concerning AEs related to bleeding at TBS and the other safety data was planned in the protocol, only 95% confidence limits on differences between treatments will be done.

Concerning safety data, an independent data review will be done by a medical reviewer before data review meeting and database lock. The medical reviewer will identify and classify all safety endpoints with respect to e.g. thrombotic events, transfusion complications, etc. and will check correctness of MeDDRA classification (PT, SOC). At the end of this review, medical reviewer will be produced a detailed report.

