6.12.6 Clinical Laboratory Data

Results for each parameter at each time point and treatment will be presented as listing, low (L) and high (H) values will be flagged in listings; in the listing will be reported the normal range of each parameter processed, too. The following table will be used for all laboratory parameters:

	STATISTICAL ANALYSIS PLAN	FSTAT.01.03
Study Code: HEM-HEM-01-17		Sealantium Medical Ltd.

1. Summary statistics in terms of number and percentages for categorized parameters will be generated by time point and treatment.
2. In case of continuous measurements descriptive statistics will be presented by time point.
3. Normal, abnormal Not Clinically Significant (NCS) and abnormal Clinically Significant (CS) counts and frequency classifications will be tabulated for all parameters having recorded data about.
4. Shift tables will show changes in frequency of normal, abnormal NCS and abnormal CS values for any post-baseline value compared to Baseline.
5. All continuous parameters will show tables with absolute change from Baseline.

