6.12.6.7 Immunogenicity - Antibodies against Human Fibrinogen and Thrombin

Values below lower limit of quantitation will be left missing for analysis. As antibody tests can undergo a second testing in case of positive tests the reconfirmed value will be taken for analysis in case of discrepancies.

Number and percentage of patients having positive/ negative results at each visit and over all visits will be tabulated.

Data on Human Antibodies against Fibrinogen and Thrombin levels will be summarized by time point with descriptive statistics for positive results.

	STATISTICAL ANALYSIS PLAN	FSTAT.01.03
Study Code: HEM-HEM-01-17		Sealantium Medical Ltd.

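### On its plain wording, the overall antibody row includes the pre-treatment Screening sample, and no newly positive rate is defined, so the row cannot be read as response to the product if any patient is positive at Screening

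*SAP*

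**What the plan says.** Antibodies against fibrinogen and thrombin are a named component of the primary safety endpoint (Protocol 12.1, SAP 3.3.1). SAP 3.3.1 gives the window: "Variables of the composite marker were assessed during all study periods: from randomization to end of follow-up".

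The schedules of assessments in both documents place antibody tests at three visits. The first is Screening, between Day -21 and Day -1, where Protocol 11.1.1 lists "Levels of antibodies against Human Fibrinogen and Human Thrombin". The other two are Visit 6 (Day 30, Protocol 11.1.6) and Visit 9 (Day 180, Protocol 11.1.9).

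For the positive/negative table, SAP 6.12.6.7 states: "Number and percentage of patients having positive/ negative results at each visit and over all visits will be tabulated". It names no visit as excluded. Levels are summarized by time point for positive results only. On low values it says: "Values below lower limit of quantitation will be left missing for analysis". Neither document defines a newly positive patient or a rate among patients negative at Screening.

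**The concern.** A reader of the safety results will take the overall row as the per-patient summary of immunogenicity in each arm. A patient who already had antibodies before surgery counts as positive in that row without any response to the patch. The same patient cannot become newly positive, and so does not belong in the denominator of a response rate. The row can therefore overstate response in an arm, and it can differ between arms because of who was enrolled. The question matters because safety is the primary objective and SAP 6.12 plans 95% confidence limits on between-arm differences in safety data.

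**Working it through.** **Method check.** The documents give no antibody rate to reproduce. The exact (Clopper-Pearson) method used below gives 51.9% to 95.7% for 12/15, which matches the 52% to 96% in Protocol 14.8.2.

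**Inputs.** 15 patients per arm (Protocol 14.1, SAP 3.4). Screening prevalence and the number of newly positive patients are not in the documents, so both are assumed. I read the overall row as ever positive at Screening, Day 30 or Day 180.

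**Step 1: overall row against newly positive rate.** Let 2 patients be newly positive and *s* other patients be positive at Screening. The overall row is (2 + *s*)/15. The newly positive rate is 2/(15 − *s*). Brackets show exact 95% limits in percent.

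| *s* | Overall row | Newly positive rate | Excess (points) |
|---|---|---|---|
| 0 | 2/15 = 13.3% (1.7–40.5) | 2/15 = 13.3% (1.7–40.5) | 0 |
| 1 | 3/15 = 20.0% (4.3–48.1) | 2/14 = 14.3% (1.8–42.8) | 5.7 |
| 2 | 4/15 = 26.7% (7.8–55.1) | 2/13 = 15.4% (1.9–45.4) | 11.3 |
| 3 | 5/15 = 33.3% (11.8–61.6) | 2/12 = 16.7% (2.1–48.4) | 16.7 |

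With no newly positive patient at all, one Screening positive gives 1/15 = 6.7% (0.2–31.9) against 0/14 = 0% (0–23.2).

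**Step 2: do the by-visit rows settle it?** Suppose 1, 2 and 2 of 15 are positive at Screening, Day 30 and Day 180. If the Screening positive stays positive at both later visits and one other patient is positive at both, 1 patient is newly positive. If the Screening positive turns negative and the later positives are four different patients, 4 are newly positive. Two and three are also possible. The same rows thus fit anything from 1/14 = 7.1% (0.2–33.9) to 4/14 = 28.6% (8.4–58.1).

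**Step 3: the denominator.** The Safety Set keeps every treated patient (SAP 4.1), patients who drop out are replaced (Protocol 7.2), and percentages use non-missing responses (SAP 6.1). Take two treated patients who left before Day 30 with only a below-limit Screening sample. If below-limit counts as negative, they enter the overall row as negatives and 2/15 = 13.3% becomes 2/17 = 11.8% (1.5–36.4). If status follows the level, and that level is left missing, they drop out. The documents do not say which applies.

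**Step 4: chance imbalance between arms.** With equal Screening prevalence in both arms, the exact binomial probability that the arms differ by 2 or more Screening positives is 18.6%, 34.5% and 48.9% at assumed prevalences of 5%, 10% and 20%. If none of these patients would otherwise count as positive, two patients are 2/15 = 13.3 points on the overall row.

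**The case against.** The strongest reply is that the plan already contains what is needed.

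- **The window.** A programmer who follows SAP 3.3.1 could start at randomization and leave Screening out, and the mock tables (SAP Appendix 2, a separate document) may say so. This stands: inclusion of Screening is the plain reading of 6.12.6.7, not an established fact.
- **Shift tables.** Item 4 of SAP 6.12.6 plans shifts from Baseline for laboratory parameters, and antibodies sit under that heading. But its categories are normal, abnormal not clinically significant and abnormal clinically significant. The hematology, biochemistry, coagulation and urine sections each call on the numbered items, while 6.12.6.7 calls on none. Item 4 may help if antibodies are classified that way, but nothing says they are.
- **Change from Baseline.** Item 5 says: "All continuous parameters will show tables with absolute change from Baseline". That gives no positive/negative rate. For a newly positive patient whose Screening level was below the limit, that level is missing under 6.12.6.7, and under SAP 6.5 "no substitution or specific approach for missing data will be applied", so no change can be computed.
- **Listings.** SAP 6.12 provides: "All Safety data will be listed by patients and treatment groups at each collected time". With about 15 patients per arm and three scheduled samples each, newly positive patients can be counted by hand. This stands in full, although it leaves the definition of the rate open until the results are known.
- **Randomization.** Let *p* be the Screening prevalence in both arms and *r* the newly positive rate among Screening-negative patients, independent of *p*. The ever-positive probability is *p* + (1 − *p*)*r*, so the expected arm difference is (1 − *p*) times the difference in *r*. It is attenuated, not reversed. This stands too. Chance imbalance remains possible at this size, but the Screening row in the same table would show it.

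**Conclusion.** The point holds as a low-severity gap in a descriptive table. On its plain wording the overall row reaches back before the endpoint window, and no planned positive/negative table clearly isolates patients who became positive after treatment. On the assumed counts the overstatement is 5.7 to 16.7 points for 1 to 3 other Screening positives. The intervals overlap widely, and the overstatement is nil if no patient is positive at Screening.

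Three stronger readings are tempting, and the documents do not support them. A reader might infer that the row certainly includes Screening; the wording suggests it, but the mock tables could restrict it. A reader might infer that the primary safety conclusion is compromised; the study tests no hypothesis, SAP 6.6 calls all results exploratory, the by-visit rows and listings preserve the data, and no decision or stopping rule uses this figure. A reader might infer that early leavers necessarily dilute the overall row; that depends on whether a below-limit result counts as negative, which is not stated.

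**What to change.** In SAP 6.12.6.7:

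(a) Report per arm and per antibody, with an exact 95% confidence interval, the proportion newly positive at Day 30 or Day 180 among Screening-negative patients with at least one post-treatment result. State that below-limit results count as negative for this purpose.

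(b) Limit the overall row to post-treatment visits. This alone does not remove a patient who was positive at Screening and stays positive, so (a) and (c) are needed as well.

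(c) Show Screening-positive patients separately, with their Screening and later levels, so that any rise is visible.

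The cost is SAP wording and one or two extra table rows per antibody, from data already collected. It needs no new visit, blood draw or protocol change. The wording should be settled before database lock, so that the rate is defined before the results are seen. How the confirmatory redraw is handled is a separate matter and not part of this point.

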6.13 Efficacy Evaluation

As described in sec. 3.3 of the SAP, efficacy evaluation will be a secondary endpoint and refers to Phase II of the study.

Note: Considering that no hypothesis testing for difference between treatments groups was planned in the protocol, only 95% confidence intervals on differences between treatments will be presented and no p-values.

All secondary and the additional endpoint variables will be listed and summarized by treatment groups and at each time will be collected.

6.13.1 Proportion of Patients achieving Hemostasis at TBS

For each patients achievement of hemostasis at TBS (absence of bleeding) at 2 (for sFilm-FS product only), 3, 5, 7 or 10 minutes following first product application will be derived. No occurrence of re-bleeding starting from 10 minutes after product application and until the completion of surgical closure must happen.

This variable, as being a time-profile in the efficacy response, will be considered to suggest a superiority in the efficacy of study drug versus control treatment. Since this is an exploratory proof of concept study and no hypothesis of extent in the difference between treatment groups a priori has been defined, we estimate the differences in the proportion of patients achieving at each time points hemostasis at TBS by the calculation of the exact 95% confidence interval (Clopper-Pearson exact method, considering the sample size) at each time point. This measure gives also a precision of the difference between treatments observed.

Beside Clopper-Pearson confidence intervals number and percentage of patients achievement of hemostasis at TBS will be tabulated by time point. The tabulation will also differ between first application and re-applications.

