10.7. Concomitant Medications

The use of any other topical hemostat, except fibrin sealants or topical thrombin, at the TBS will be permitted once the observational period is completed and hemostasis was not achieved or in the event of breakthrough bleeding requiring further treatment (as deemed necessary by the Investigator).

For additional bleeding sites, separate from the TBS, patients must be treated with the same study article according to the randomization assignment, when clinically appropriate. If other hemostatic products are needed the Investigator should revert to his/her standard of care (excluding fibrin sealants and topical thrombin).

Administration of all medications, including indication, dose, frequency, and route of administration will be recorded in the source documentation file and in the electronic Case Report Form (eCRF). All concomitant medications will be discussed and documented at each visit.

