Hemostasis is defined as an absence/cessation of bleeding at the TBS according to the surgeon's judgement, so that the surgical closure of the field could be started. Time to hemostasis (TTH) is defined as time until hemostasis is achieved. **TTHP** will be considered as time from first product application and **TTHR** as time from randomization will be collected as well but will not be used as endpoint.

Treatment failure is defined as follows:

- in case the bleeding at TBS (or re-bleeding) is still observed after 10 minutes following first application of product;
- if hemostasis at TBS is achieved, but the Investigator decides that an additional treatment is required to ensure the durability of hemostasis;
- if there is a breakthrough bleeding requiring treatment other than the product, at any time.

In case of treatment failure, the Investigator may revert the treatment to standard of care. If additional sites requiring a topical hemostasis product are identified after the treatment of the initial target bleeding site, these bleeding sites should be treated with the same treatment article according to the patient's randomization assignment, if clinically appropriate. If other hemostatic products are needed, the Investigator should revert to his/her standard of care (excluding fibrin sealants or topical thrombin).

The following information will be collected during surgery and recorded on the eCRF and in the study file:

- Determination of hemostasis at TBS.
- Use of other hemostatic measures.
- Collection of intra-operative details including hepatic parenchyma classification type (normal or abnormal, steatotic, cirrhotic or other), Investigator description of the TBS (area, density, arterial/venous/mixed, intensity of flow), alternative methods used to achieve hemostasis (if applicable), estimated TBS treated area and total resected area, number of product units applied at the TBS and at other areas rather than the TBS, incidence of post-operative bile leaks requiring intervention, hepatic segment information (anatomic resection/non-anatomic resection).
- Collection of operative/surgical information, including OR time, procedure time, time from liver resection/incision to initiation of fascial closure, drain usage, estimated blood loss, cell salvage use, transfusion information (if applicable), length of stay (ICU and overall LOS).

Additional assessments will be taken at the end of surgery and will include the following:

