3.3.2 Secondary Endpoints

The secondary endpoints of the study are:

- The proportion of patients achieving hemostasis at TBS: at 2 (for sFilm-FS product only) 3, 5, 7 or 10 minutes following first product application, without the occurrence of re-bleeding, starting from 10 minutes after product application and until the completion of surgical closure. Hemostasis at TBS is defined as: absence of bleeding without the occurrence of re-bleeding.
- The incidence of re-treatment (defined as one or more additional patch of sFilm-FS or TACHOSIL®) at the TBS at the different time points (2 for sFilm-FS only, 3, 5, 7, 10 minutes from first product application).
- The Time to Hemostasis from first product application (TTHP).
- The proportion of all patients that have achieved hemostasis 10 minutes after first product application and therefore did not need to convert to standard of care treatment at the end of these 10 minutes. This includes all patients that achieved hemostasis with a single patch application and patients that required additional patches.
- The incidence of treatment failure. Treatment failure is defined as follows:

	STATISTICAL ANALYSIS PLAN	FSTAT.01.03
Study Code: HEM-HEM-01-17	Sealantium Medical Ltd.	

1. in case the bleeding at TBS (or re-bleeding) is still observed after 10 minutes following first application of product
2. if hemostasis at TBS is achieved, but the Investigator decides that and additional treatment is required to ensure the durability of hemostasis
3. if there is a breakthrough bleeding requiring treatment other than the product, at any time

From treatment failures definition are excluded those re-bleeding arising from the target bleeding site after hemostasis has been reached, and that are caused by movement of patch from the wound (caused by the surgeon or any other possible external factor) or other external factors. These cases should be regarded as Adverse Events rather than treatment failures. See Sponsor MEMO "*Clarification on treatment failure vs AE*" (AE=adverse event) dated 12th April 2022.

- The incidence of transfusion requirements in the 6 months follow-up period.

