6.13.3 Time to Hemostasis from first Product Application (TTHP)

Time to Hemostasis from first product application (TTHP) (minutes) is defined as the difference between time point of first product application during surgery until time point of reaching hemostasis. Descriptive statistics for TTHP will be shown.

For time-to-event analysis of TTHP, an event is defined as reaching hemostasis. In case no hemostasis has been reached the patient will be censored at 10 minutes. That means that in case that further patches have to be applied the clock for determination of TTHP is

	STATISTICAL ANALYSIS PLAN	FSTAT.01.03
Study Code: HEM-HEM-01-17	Sealantium Medical Ltd.	

prolonged. Kaplan-Meier curves for TTHP for each treatment will be generated. Tabulations will include number and percentage of patients failed and censored, median time to hemostasis with 95% confidence limits, first and third percentile, minimum and maximum time, estimates for 2-minute, 3-minute, 5- minute, 7 minute and 10 minute TTHP hemostasis incidence. Hazard ratio including confidence interval for sFilm-FS versus Tachosil® will be tabulated. Note that to connect correct estimation of hemostasis incidences to the estimations delivered by the survival model, a survival probability denotes the non-occurrence probability of hemostasis.

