6.13.4 Time to Hemostasis from Patient Randomization (TTHR)

Time to Hemostasis from patient randomization (TTHR) (minutes) will be collected and displayed with descriptive statistics. TTHR is defined as time from randomization until hemostasis (in case of event) or 10 minutes observation end in case of censoring. Kaplan-Meier curve will be used to estimate the median TTHR in each treatment group. KM parameters and analyses will be tabulated in an analogue manner like in sec. 6.13.3.

6.13.5 Percentage of all Patients who achieved Hemostasis at 10 Minutes after first Product Application

Number and percentage of all patients (patients that achieved hemostasis with a single patch application and patients that required additional patches) that have achieved hemostasis 10 minutes after first product application and therefore did not need to convert to standard of care treatment at the end of these 10 minutes will be tabulated.

Data will be presented with descriptive statistics and 95% confidence intervals of the difference between treatments.

A stratified analyses by one-patch applicants and more than one patch users may be done depending on the results of the BDRM using strata single patch users and additional patch users. In case it is decided to perform a stratified analysis a table will be added to show number/ percentages of patients with one patch and with >1 patches.

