6.13.6 Incidence of Treatment Failure

Incidence of treatment failure is defined on treatment failure criteria according to section 11.1.3 of the protocol:

- in case the bleeding at TBS (or re-bleeding) is still observed after 10 minutes following first application of study product;
- if hemostasis at TBS is achieved, but the Investigator decides that an additional treatment is required to ensure the durability of hemostasis;
- if there is a breakthrough bleeding requiring treatment other than the study product, at any time

Data will be presented only with the appropriate descriptive statistics and exact Clopper Pearson 95% confidence interval of the difference between treatments

	STATISTICAL ANALYSIS PLAN	FSTAT.01.03
Study Code: HEM-HEM-01-17		Sealantium Medical Ltd.

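### A patient dried by a non-study hemostat before 10 minutes counts as a hemostasis success at later time points and as a treatment failure, because SAP 6.13.1 and 6.13.3 have no rule for rescue

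*SAP*

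**What the plan says.** - **Definition.** Protocol 11.1.3: "Hemostasis is defined as an absence/cessation of bleeding at the TBS according to the" judgement of the surgeon. It does not say what must have stopped the bleeding.
- **Proportions.** SAP 6.13.1 derives "For each patients achievement of hemostasis at TBS (absence of bleeding) at 2 (for sFilm-FS product only), 3, 5, 7 or 10 minutes" after first application. Its one added condition is "No occurrence of re-bleeding starting from 10 minutes after product application and until the completion of surgical closure must happen".
- **Shorter definition.** SAP 3.3.2 adds "Hemostasis at TBS is defined as: absence of bleeding without the occurrence of re-bleeding". This sentence has no time window, but the one before it carries the window from 10 minutes to closure.
- **Time to hemostasis (TTHP).** SAP 6.13.3: "an event is defined as reaching hemostasis. In case no hemostasis has been reached the patient will be censored at 10 minutes". SAP 6.13.4 treats time from randomization in the same way.
- **Ten-minute percentage.** SAP 6.13.5 counts those "that have achieved hemostasis 10 minutes after first product application and therefore did not need to convert to standard of care treatment"; it refers to conversion only when the 10 minutes are over. It describes them as single-patch patients and patients who needed more patches.
- **Non-study hemostats.** Protocol 10.7 allows one at the TBS on either of two grounds: the observation period has ended without hemostasis, "or in the event of breakthrough bleeding requiring further treatment (as deemed necessary by the Investigator)". The second ground has no time limit.
- **Treatment failure.** The third criterion in SAP 6.13.6 is "if there is a breakthrough bleeding requiring treatment other than the study product, at any time". The second covers sites where hemostasis was achieved but the investigator adds treatment to make it last.

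**The concern.** The protocol synopsis says the secondary endpoints concern the hemostatic efficacy of the product. The derivation rules, however, ask only whether the site is dry. If a non-study hemostat stops the bleeding inside the 10-minute window, the patient is credited as a hemostasis success from then on, although the assigned patch did not control the bleeding.

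A successful rescue can only raise the apparent hemostasis rate of the arm that uses it. The surgeon knows the product and judges both breakthrough and hemostasis, so rescue need not be used equally in the two arms. SAP 6.13.1 intends to read this time profile as a suggestion of superiority over the comparator, and SAP 6.13.3 adds a hazard ratio. With 15 patients per arm, one or two such patients would be visible in the estimates.

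**Working it through.** **1. The plan's own figure.** Protocol 14.8.2 gives an exact 95% CI of 52% to 96% for 80% of 15 patients. The Clopper-Pearson limits for x of n are the 0.025 quantile of Beta(x, n−x+1) and the 0.975 quantile of Beta(x+1, n−x). For x = 12, n = 15 they are 51.9% and 95.7%, so the figure is reproduced.

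**2. Two hypothetical patients traced through the rules.** Both break through at 4 minutes, receive a non-study hemostat, are dry at 5, 7 and 10 minutes, and do not bleed again before closure.

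| Rule | A: patch held at 3 min, then broke through | B: never dry until rescued |
|---|---|---|
| SAP 6.13.1, 5, 7 and 10 min | success | success |
| SAP 6.13.3, TTHP | event at 3 min, before the rescue | event when dried by the rescue |
| SAP 6.13.6, third criterion | failure | failure |
| SAP 3.3.2 sentence, read without the window | excluded as re-bleeding | not excluded: nothing re-bled |
| SAP 3.3.2 sentence, read with the window | not excluded | not excluded |

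Both are success and failure under 6.13.1 and 6.13.6. TTHP credits the rescue only for patient B.

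**3. Effect on a proportion.** Each patient is worth 1/15 = 6.7 points. Suppose 12 of 15 are dry at 10 minutes under the SAP wording and k of them were dried by a non-study hemostat. The values of k are assumptions.

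| k | Reported | Study product only | Exact 95% CI | Successes + failures (12 + 3 + k) |
|---|---|---|---|---|
| 0 | 12/15 = 80.0% | 12/15 = 80.0% | 51.9 to 95.7 | 15 |
| 1 | 12/15 = 80.0% | 11/15 = 73.3% | 44.9 to 92.2 | 16 |
| 2 | 12/15 = 80.0% | 10/15 = 66.7% | 38.4 to 88.2 | 17 |
| 3 | 12/15 = 80.0% | 9/15 = 60.0% | 32.3 to 83.7 | 18 |

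**4. Effect on TTHP.** Hypothetical arm of 15: study product dries 7 at 3 min, 2 at 5 min and 1 at 7 min; two type-B patients are rescued at 6 min and dry at 7; three are never dry. With S(t) = ∏(1 − d/n):
- S(3) = 1 − 7/15 = 0.533; S(5) = 0.533 × (1 − 2/8) = 0.400.
- SAP wording: S(7) = 0.400 × (1 − 3/6) = 0.200, incidence 80.0%.
- Rescued patients kept as non-events to 10 min: S(7) = 0.400 × (1 − 1/6) = 0.333, incidence 66.7%.
- Rescued patients censored at 6 min: S(7) = 0.400 × (1 − 1/4) = 0.300, incidence 70.0%. Censoring at rescue still overstates the product.

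The median is 5 min in all three.

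**5. The 3-minute result.** Protocol 11.1.3 requires at least 3 minutes of compression for TACHOSIL and at least 2 for sFilm-FS, with 2 more if the site is not dry. There is little room for a non-study hemostat before the 3-minute reading.

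**The case against.** **The route is narrow.** For bleeding that persists inside the window, Protocol 11.1.3 describes more compression and re-application of the study product, and the first ground in Protocol 10.7 defers other hemostats until observation ends. Early rescue rests on breakthrough bleeding, which is not defined. This stands: few patients may be affected, and patient B depends on how that term is applied. It does not close the route.

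**SAP 3.3.2 already excludes re-bleeding.** On one reading it removes patient A. It conflicts with the 10-minute window in the sentence before it and in 6.13.1, and it does not reach patient B. It needs reconciling.

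**SAP 6.13.5 already refers to study patches.** It names single-patch and additional-patch patients, so it arguably leaves out a patient dried by something else. This largely stands for that endpoint. Its remark on conversion to standard of care is worded as a consequence and only for the end of the 10 minutes, so it is not an exclusion rule, and it does not govern 6.13.1 or 6.13.3.

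**Hemostasis and failure may coexist.** The second failure criterion says so. This stands for treatment added for durability; it does not justify crediting the patch where other treatment stopped the bleeding.

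**The failure table would show the discrepancy.** Partly. SAP 3.3.2 moves re-bleeding caused by patch movement or other external factors from treatment failure to adverse events, so some rescued patients might appear in neither place.

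**A reader might infer more from SAP 6.13.3.** Its remark that the clock is prolonged could suggest that a site dried by rescue at 12 minutes enters as an event at 12. The text ties the prolongation to further patches and does not mention rescue, so that inference is not supported.

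**Conclusion.** The gap is real. SAP 6.13.1 credits as success a patient dried by a non-study hemostat before 10 minutes, and 6.13.3 does so when hemostasis was first reached through that treatment. The same patient meets the third failure criterion. The double count follows from a missing rule; the documents do not state it outright.

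Each such patient shifts an arm of 15 by 6.7 points. With two among 12 apparent successes, 80% (52 to 96%) becomes 67% (38 to 88%). These counts are assumptions: no rescue rate is given, and with none nothing changes.

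A reader might conclude that efficacy as a whole measures patch plus any rescue, or that the lead result is compromised. The documents do not support this. Early non-study treatment is confined to breakthrough bleeding, the 3-minute proportion has little room to be affected, and Protocol 14.5 and SAP 6.6 make efficacy untested and exploratory. Severity is moderate.

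**What to change.** - **SAP 6.13.1, and for clarity 6.13.5:** count a patient given a non-study hemostatic treatment for bleeding at the TBS as not in hemostasis at every time point from that treatment onward. Reconcile this with the re-bleeding sentence in SAP 3.3.2.
- **SAP 6.13.3 and 6.13.4:** define the event as hemostasis reached with study product only. Keep patients rescued before hemostasis as non-events to the end of the 10-minute window; do not censor them at rescue.
- **Consistency check:** cross-tabulate 10-minute hemostasis against treatment failure. Report patients under the second failure criterion separately, since the documents let both hold for them.
- **Data check:** the protocol has other hemostatic measures recorded, but does not show that their time is. Confirm this in the eCRF. If the time is missing, count such patients as non-successes at 10 minutes in a sensitivity table.

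This is an analysis rule and leaves clinical management unchanged. If the times are recorded, the cost is SAP wording and programming before database lock. The 5-, 7- and 10-minute figures may be slightly lower.
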